3.4.5 Potential Drug Interactions

Cytochrome P450 (CYP): Data from a clinical drug interaction study (Study XL184-008) show that clinically relevant steady-state concentrations of cabozantinib appear to have no marked effect on the area under the plasma drug concentration time curve (AUC) of co-administered rosiglitazone, a CYP2C8 substrate. Therefore, cabozantinib is not anticipated to markedly inhibit CYP2C8 in the clinic, and by inference, is not anticipated to markedly inhibit other CYP450 isozymes that have lower [I]/Ki values compared with CYP2C8 (ie, CYP2C9, CYP2C19, CYP2D6, CYP1A2, and CYP3A4). In vitro data indicate that cabozantinib is unlikely to induce cytochrome P450 enzymes, except for possible induction of CYP1A1 at high cabozantinib concentrations (30 μM).

Cabozantinib is a CYP3A4 substrate and a weak substrate for CYP2C9 (but not a CYP2D6, CYP2C8, CYP2C19, CYP2B6, or CYP1A2 substrate), based on data from in

vitro studies. Results from a clinical pharmacology study, XL184-006, showed that concurrent administration of cabozantinib with the strong CYP3A4 inducer, rifampin, resulted in an approximately 77% reduction in cabozantinib exposure (AUC values) after a single dose of cabozantinib in healthy volunteers. Chronic co-administration of cabozantinib with strong inducers of the CYP3A4 family (eg, dexamethasone, phenytoin, carbamazepine, rifampin, rifabutin, rifapentine, phenobarbital, and St. John's Wort) may significantly decrease cabozantinib concentrations. The chronic use of strong CYP3A4 inducers should be avoided. Other drugs that induce CYP3A4 should be used with caution because these drugs have the potential to decrease exposure (AUC) to cabozantinib. Selection of alternate concomitant medications with no or minimal CYP3A4 enzyme induction potential is recommended.

Results from a clinical pharmacology study, XL184-007, showed that concurrent administration of cabozantinib with the strong CYP3A4 inhibitor, ketoconazole, resulted in a 38% increase in the cabozantinib exposure (AUC values) after a single dose of cabozantinib in healthy volunteers. Co-administration of cabozantinib with strong inhibitors of the CYP3A4 family (eg, ketoconazole, itraconazole, clarithromycin, indinavir, nefazodone, nelfinavir, and ritonavir) may increase cabozantinib concentrations. Grapefruit and Seville oranges may also increase plasma concentrations of cabozantinib and should be avoided. Strong CYP3A4 inhibitors should be avoided and other drugs that inhibit CYP3A4 should be used with caution because these drugs have the potential to increase exposure (AUC) to cabozantinib. Selection of alternate concomitant medications with no or minimal CYP3A4 enzyme inhibition potential is recommended.

In addition, cimetidine should be avoided because of its potential to interfere with CYP3A4 mediated metabolism of cabozantinib.

Please refer to the drug interaction tables at the following websites for lists of substrates, inducers, and inhibitors of selected CYP450 isozyme pathways:

Http://medicine.iupui.edu/clinpharm/ddis/table.aspx

 $\underline{http://www.fda.gov/Drugs/DevelopmentApprovalProcess/DevelopmentResources/DrugIn}\\ \underline{teractionsLabeling/ucm080499.htm}$

Protein Binding: Cabozantinib is highly bound (\geq 99.7%) to human plasma proteins. Therefore, highly protein bound drugs should be used with caution with cabozantinib

because there is a potential displacement interaction that could increase free concentrations of cabozantinib and/or a co-administered highly protein-bound drug (and a corresponding increase in pharmacologic effect).

Other Interactions: Food may increase exposure levels of cabozantinib by 57%, fasting recommendations should be followed. In vitro data suggest that cabozantinib is unlikely to be a substrate for P-glycoprotein, but it does appear to have the potential to inhibit the P-glycoprotein transport activity. Therefore, cabozantinib may have the potential to increase plasma concentrations of co-administered substrates of P-glycoprotein. Additional details related to these overall conclusions can be found in the investigator brochure.

Additional details regarding potential drug interactions with cabozantinib can be found in the investigator brochure.

3.5 Compliance

Drug accountability and subject compliance will be assessed with drug dispensing and return records.

3.6 Study Drug Accountability

The investigator will maintain accurate records of receipt of all cabozantinib, including dates of receipt. In addition, accurate records will be kept regarding when and how much study treatment is dispensed and used by each subject in the study. Reasons for deviation from the expected dispensing regimen must also be recorded. At completion of the study, to satisfy regulatory requirements regarding drug accountability, all unused cabozantinib will be reconciled and destroyed in accordance with applicable state and federal regulations.

4 STUDY POPULATION

4.1 Inclusion Criteria

Malignant PH and PG patients will be eligible for enrollment as defined by the inclusion and exclusion criteria as follows:

- 1. 18 years of age or older
- 2. Histological confirmation of PH/PG
- 3. Locally advanced or metastatic disease not amenable to surgery
- 4. Patients enrolled in the main branch should have measurable disease. Patients with a predominance of bone disease who have small, non-measurable or small measurable lesions other than bone, may be included per the Principal

- Investigator's discretion, in the exploratory branch of the study for patients with bone metastases only.
- 5. Progressive disease per RECIST 1.1 as determined by the investigator within the 12 months preceding study enrollment
- 6. Assessment of all known disease sites, eg, by computerized tomography (CT) scan, magnetic resonance imaging (MRI), bone scan as appropriate, and/or FDG-PET scan within 28 days before the first dose of cabozantinib
- 7. Eastern Cooperative Oncology Group (ECOG) performance status of ≤ 2 .
- 8. Life expectancy of at least 3 months
- 9. Organ and marrow function and laboratory values as follows within 4 days prior to the first dose of cabozantinib:
 - a. Absolute neutrophil count (ANC) $\geq 1500/\text{mm}^3$ without colony stimulating factor support
 - b. Platelets $\geq 100,000/\text{mm}^3$
 - c. Hemoglobin $\geq 9 \text{ g/dL}$
 - d. Bilirubin $\leq 1.5 \times$ the upper limit of normal (ULN). For subjects with known Gilbert's disease, bilirubin $\leq 3.0 \text{ mg/dL}$
 - e. Serum albumin $\geq 2.8 \text{ g/dl}$
 - f. Serum creatinine $\leq 1.5 \times ULN$ or creatinine clearance (CrCl) ≥ 50 mL/min. For creatinine clearance estimation, the Cockcroft and Gault equation should be used:

Male: $CrCl (mL/min) = (140 - age) \times wt (kg) / (serum creatinine \times 72)$ Female: Multiply above result by 0.85

- g. Alanine aminotransferase (ALT) and aspartate aminotransferase (AST) $\leq 3.0 \times \text{ULN}$
- h. Lipase < 2.0 x the upper limit of normal and no radiologic or clinical evidence of pancreatitis
- i. Urine protein/creatinine ratio (UPCR) ≤ 1
- j. Serum phosphorus, calcium, potassium \geq LLN and magnesium \geq 1.2 mg/dL
- 10. Capable of understanding and complying with the protocol requirements and has signed the informed consent document.
- 11. Sexually active patients (men and women) must agree to use medically accepted barrier methods of contraception (eg, male or female condom) during the course of the study and for 4 months after the last dose of study drug(s), even if oral contraceptives are also used. All subjects of reproductive potential must agree to use both a barrier method and a second method of birth control during the course of the study and for 4 months after the last dose of study drug(s).

12. Women of childbearing potential must have a negative pregnancy test at screening. Women of childbearing potential include women who have experienced menarche and who have not undergone successful surgical sterilization (hysterectomy, bilateral tubal ligation, or bilateral oophorectomy) or are not postmenopausal. Postmenopause is defined as amenorrhea ≥ 12 consecutive months. Note: women who have been amenorrheic for 12 or more months are still considered to be of childbearing potential if the amenorrhea is possibly due to prior chemotherapy, antiestrogens, ovarian suppression or any other reversible reason.

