2.2 Study Design

2.2.1 Overview of Study Design

This is a single-arm, open-label phase II study of cabozantinib in subjects with malignant pheochromocytomas and paragangliomas. The primary endpoint is to estimate best overall response rate by RECIST 1.113 in patients with measurable disease determined by a. CT or b. MRI.

The primary objective is to estimate the best overall response rate in patients with measurable disease. Response will include RECIST 1.1 CR, PR, and SD. With 14 patients, the 95% confidence interval for a 45% response rate would be (18.9, 71.1%). For the exploratory objective in the small group of patients with bone metastases, the 95% confidence interval for a 45% response rate with 8 patients would be (10.5, 79.5%). We do not include a formal statistical monitoring rule for toxicity given the established safety profile of this drug.

Continuous variables will be summarized using descriptive statistics such as mean, standard deviation, median and range. Categorical variables will be tabulated by frequencies and the corresponding percentages. Response rates and their 95% confidence intervals will be estimated. Kaplan Meier survival curves will be used to estimate survival outcomes. Cox proportional hazards regression analysis may be used to assess the association between survival and covariates of interest. The Fisher's exact test or logistic regression analysis will be used for any binary outcomes. T-tests or Wilcoxon rank sum tests will be used to compare continuous variables. Longitudinal models may be explored to study change over time.

Each subject's course will consist of three periods:

- A Pre-Treatment Period in which subjects are consented and undergo screening assessments to be qualified for the study (Section 5.1);
- A Treatment Period in which subjects receive study treatment and undergo study assessments (Section 5.2);

• A Post-Treatment Period in which subjects no longer receive study treatment but undergo follow-up study assessments and contacts (Section 5.3).

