4.2 Exclusion Criteria

A subject who meets any of the following criteria is ineligible for the study:

- 1. Received cytotoxic chemotherapy (including investigational cytotoxic chemotherapy) or biologic agents (eg, cytokines or antibodies) within 3 weeks, or nitrosoureas/ mitomycin C within 6 weeks before the first dose of study treatment.
- 2. Prior treatment with cabozantinib
- 3. Radiation therapy for bone metastasis within 2 weeks, any other external radiation therapy within 4 weeks before the first dose of study treatment. Subjects with clinically relevant ongoing complications from prior radiation therapy are not eligible;
- 4. Received radionuclide treatment (i.e. I ¹³¹ meta-iodo- benzyl guanidine) within 6 months of the first dose of study treatment
- 5. Receipt of any type of small molecule kinase inhibitor (including investigational kinase inhibitor) within 14 days before the first dose of study treatment.
- 6. Receipt of any other type of investigational agent within 28 days before the first dose of study treatment.
- 7. The subject has not recovered to baseline or CTCAE ≤ Grade 1 from toxicity due to all prior therapies except alopecia and other non-clinically significant AEs.
- 8. Prothrombin time (PT)/ International Normalized Ratio (INR) or partial thromboplastin time (PTT) test ≥ 1.3 × the laboratory ULN within 7 days before the first dose of study treatment.
- 9. The subject requires concomitant treatment, in therapeutic doses, with anticoagulants such as warfarin or warfarin-related agents, heparin, thrombin or Factor Xa inhibitors, or antiplatelet agents (eg, clopidogrel). Low dose aspirin (≤ 81 mg/day), low-dose warfarin (≤ 1 mg/day), and prophylactic low molecular weight heparin (LMWH) are permitted.
- 10. The subject requires chronic concomitant treatment of strong CYP3A4 inducers (eg, dexamethasone, phenytoin, carbamazepine, rifampin, rifabutin, rifapentin, phenobarbital, and St. John's Wort).
- 11. The subject has experienced any of the following:
 - a. clinically-significant gastrointestinal bleeding within 6 months before the first dose of study treatment

- b. hemoptysis of ≥ 0.5 teaspoon (2.5ml) of red blood within 3 months before the first dose of study treatment
- c. any other signs indicative of pulmonary hemorrhage within 3 months before the first dose of study treatment
- 12. Radiographic evidence of cavitating pulmonary lesion(s)
- 13. Tumor invading or encasing any major blood vessels

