7 STATISTICAL CONSIDERATIONS

This Phase II study's primary objective is to estimate the best overall response rate in patients with measurable disease. Response will include RECIST 1.1 CR, PR, and SD. With 14 patients, the 95% confidence interval for a 45% response rate would be (18.9, 71.1%). For the exploratory objective in the small group of patients with bone metastases, the 95% confidence interval for a 45% response rate with 8 patients would be (10.5, 79.5%). We do not include a formal statistical monitoring rule for toxicity given the established safety profile of this drug.

Continuous variables will be summarized using descriptive statistics such as mean, standard deviation, median and range. Categorical variables will be tabulated by frequencies and the corresponding percentages. Response rates and their 95% confidence intervals will be estimated. Kaplan Meier survival curves will be used to estimate survival outcomes. Cox proportional hazards regression analysis may be used to assess the association between survival and covariates of interest. The Fisher's exact test or logistic regression analysis will be used for any binary outcomes. T-tests or Wilcoxon rank sum tests will be used to compare continuous variables. Longitudinal models may be explored to study change over time.

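### Inclusion criterion 5 does not tie the qualifying progression to the most recent therapy, so disease control carried over from earlier treatment can be counted as response

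*Combined protocol and SAP*

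**What the plan says.** The entry criterion is section 4.1, item 5, repeated in the synopsis: "Progressive disease per RECIST 1.1 as determined by the investigator within the 12 months preceding study enrollment". It sets a time window and does not mention prior treatment.

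Prior treatment is handled only through the washouts in section 4.2:

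- Item 1, cytotoxic chemotherapy: 3 weeks. The same item continues "or biologic agents (eg, cytokines or antibodies) within 3 weeks, or nitrosoureas/ mitomycin C within 6 weeks before the first dose of study treatment".
- Item 3, external radiation: 2 weeks for bone metastases, 4 weeks otherwise.
- Item 4, radionuclides: excluded if given "within 6 months of the first dose of study treatment".
- Item 5: "Receipt of any type of small molecule kinase inhibitor (including investigational kinase inhibitor) within 14 days before the first dose of study treatment".
- Item 6, other investigational agents: 28 days.

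Section 4.1, item 6, asks for imaging of known disease within 28 days before the first dose, but that scan need not show growth against an earlier one. Section 5.1 rechecks the same criteria on Day 1 and adds no growth requirement.

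On the endpoint, section 7 states "Response will include RECIST 1.1 CR, PR, and SD". Section 5.5 puts tumor assessments every 8 weeks in the first year, and the plan gives no minimum duration for stable disease. Section 2.1 makes 1-year PFS a secondary endpoint in all patients. On design, section 2.2.1 states "This is a single-arm, open-label phase II study of cabozantinib in subjects with malignant pheochromocytomas and paragangliomas".

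**The concern.** The progression criterion is what makes stable disease on treatment informative: if a tumor was growing at entry and then stops, the drug is a plausible cause. That reasoning fails for a patient whose growth had already been stopped by something else.

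Two patients who meet the criteria on these points show how this can happen. One progresses 11 months before entry, receives a radionuclide 7 months before, and has been stable since. The other progresses 11 months before entry, has chemotherapy from month 10 until 4 weeks before the first dose, and is stable at baseline. Neither is progressing on Day 1. If either is still stable at week 8, the plan records a response.

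The primary rate and 1-year PFS would then partly describe an earlier treatment. With one arm, nothing in the design separates the two. Previously treated patients are to be expected: the hypothesis in section 1.1 concerns resistance after sunitinib, and prior kinase inhibitors are allowed after 14 days. The criteria do not distinguish a patient who progressed on such a drug from one who stopped it while controlled.

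**Working it through.** **Step 1: reproduce the plan's figures.** The plan states "With 14 patients, the 95% confidence interval for a 45% response rate would be (18.9, 71.1"%), and for the bone-only branch "the 95% confidence interval for a 45% response rate with 8 patients would be (10.5, 79.5"%). The formula is p ± 1.96 × √(p(1 − p)/n) with p = 0.45.

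- n = 14: 1.96 × √(0.2475/14) = 0.261, giving 18.9% to 71.1%.
- n = 8: 1.96 × √(0.2475/8) = 0.345, giving 10.5% to 79.5%.

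Both agree. No stated figure is wrong.

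**Step 2: room for an intervening therapy.** This is 12 months less the washout, counting enrollment and first dose as the same time and a month as 30.44 days.

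| Prior therapy | Washout | Time left |
|---|---|---|
| Kinase inhibitor | 14 days | 11.5 months |
| Chemotherapy or biologic | 3 weeks | 11.3 months |
| Nitrosourea or mitomycin C | 6 weeks | 10.6 months |
| Radionuclide | 6 months | 6 months |

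Every washout leaves time to progress, be treated and be controlled before entry.

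**Step 3: effect on the primary rate.** Let t be the response rate in patients without carried-over control, k the number of the 14 who enter with it, and c their chance of being scored at least stable. Then

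expected rate = ((14 − k)t + kc)/14, and inflation = k(c − t)/14.

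Here k, c and t are assumptions; only n = 14 and the planning value of 45% come from the plan.

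| True t | c | k = 1 | k = 2 | k = 3 |
|---|---|---|---|---|
| 30% | 1.0 | 35.0% | 40.0% | 45.0% |
| 30% | 0.8 | 33.6% | 37.1% | 40.7% |
| 45% | 1.0 | 48.9% | 52.9% | 56.8% |
| 45% | 0.8 | 47.5% | 50.0% | 52.5% |

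With c = 1, inflation per patient is 0.70/14 = 5.0 points at t = 30% and 0.55/14 = 3.9 points at t = 45%. With c = 0.8 it is 0.50/14 = 3.6 and 0.35/14 = 2.5 points. It vanishes when c = t. The ceiling is 1/14 = 7.1 points, reached only if c = 1 and t = 0.

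**Step 4: read backwards.** If the observed rate is 45% and c = 1, the rate in the other patients is (6.3 − k)/(14 − k): 40.8%, 35.8% and 30.0% for k = 1, 2 and 3.

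**The case against.** The strongest reply is that a look-back window alone is a recognized form. The phase 3 medullary thyroid trial described in section 1.2.3.1 required progression within 14 months of randomization. In addition, the stated primary objective concerns patients with measurable disease, not disease growing at entry. There is no null rate or decision rule, and the planned interval is already about ±26 points. This shows that the wording is a design choice and not an error. It does not answer the point, because that phase 3 trial had a placebo arm and this one has none. Sampling width also does not excuse a shift in what is being estimated.

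Four stronger readings are tempting, and the documents do not support them.

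- A reader might infer that carried-over control is being counted. The criteria permit such patients but do not show that any were enrolled.
- A reader might take 7.1 points per patient (21.4 for three) as the bias. That is the patient's whole share of the numerator. The expected inflation for three is 15.0 points at a true 30% and 11.8 at 45%, even with c = 1.
- A reader might infer that partial responses are affected equally. A partial response needs shrinkage from a baseline taken after the washout, so the mechanism acts mainly through stable disease. Reporting CR plus PR separately would remove most of it, though not delayed shrinkage or the effect on PFS.
- A reader might want progression after any therapy, local included. Section 1.1 says palliative radiation is often needed, and exclusion 3 allows bone radiation up to 2 weeks before dosing. Such a rule would bar a patient with true systemic progression who then had one bone lesion irradiated.

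**Conclusion.** The gap in the text is certain: the plan never requires progression during or after the most recent therapy, and the washouts do not supply that requirement. The consequence is possible and not demonstrated. Carried-over control can be counted as response, mainly as stable disease, and can inflate 1-year PFS; the size of the PFS effect cannot be computed from the documents. The figures for the primary rate (5.0 or 3.9 points per patient, and a true 30% reading as 45% with three) rest on assumed values of k, c and t. The washouts, above all the 6 months for radionuclides, make carry-over less likely without excluding it. This is a worthwhile and inexpensive improvement to what a single-arm rate can support. It does not invalidate the sample size or the planned intervals.

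**What to change.** **Whatever the enrollment status.** Before responses are tabulated, use source records of prior-therapy and progression dates to flag each patient who lacks documented progression during or after the most recent systemic or radionuclide therapy. Patients never given such therapy are not flagged; those whose dates cannot be established should be listed as undetermined. Prespecify in section 7 that the primary rate and 1-year PFS are reported with and without flagged patients.

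**If enrollment is still open.** Amend item 5 in section 4.1 and the synopsis so that the qualifying progression, still within 12 months, is shown on imaging obtained during or after the most recent systemic or radionuclide therapy. Palliative local treatment of a non-target site should not restart the requirement.

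**Cost.** The flag needs a modest record check. Table 5-1 lists a medical and cancer history, but section 12.3 leaves some data in source documents only, so the dates may not be in the eCRF. The restricted estimate is less precise: with three patients removed, the half-width at 45% goes from 26.1 points to 1.96 × √(0.2475/11) = 29.4 points. The amendment would slow accrual somewhat, which matters at a single site in a rare tumor.

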4.2 Exclusion Criteria

A subject who meets any of the following criteria is ineligible for the study:

- 1. Received cytotoxic chemotherapy (including investigational cytotoxic chemotherapy) or biologic agents (eg, cytokines or antibodies) within 3 weeks, or nitrosoureas/ mitomycin C within 6 weeks before the first dose of study treatment.
- 2. Prior treatment with cabozantinib
- 3. Radiation therapy for bone metastasis within 2 weeks, any other external radiation therapy within 4 weeks before the first dose of study treatment. Subjects with clinically relevant ongoing complications from prior radiation therapy are not eligible;
- 4. Received radionuclide treatment (i.e. I ¹³¹ meta-iodo- benzyl guanidine) within 6 months of the first dose of study treatment
- 5. Receipt of any type of small molecule kinase inhibitor (including investigational kinase inhibitor) within 14 days before the first dose of study treatment.
- 6. Receipt of any other type of investigational agent within 28 days before the first dose of study treatment.
- 7. The subject has not recovered to baseline or CTCAE ≤ Grade 1 from toxicity due to all prior therapies except alopecia and other non-clinically significant AEs.
- 8. Prothrombin time (PT)/ International Normalized Ratio (INR) or partial thromboplastin time (PTT) test ≥ 1.3 × the laboratory ULN within 7 days before the first dose of study treatment.
- 9. The subject requires concomitant treatment, in therapeutic doses, with anticoagulants such as warfarin or warfarin-related agents, heparin, thrombin or Factor Xa inhibitors, or antiplatelet agents (eg, clopidogrel). Low dose aspirin (≤ 81 mg/day), low-dose warfarin (≤ 1 mg/day), and prophylactic low molecular weight heparin (LMWH) are permitted.
- 10. The subject requires chronic concomitant treatment of strong CYP3A4 inducers (eg, dexamethasone, phenytoin, carbamazepine, rifampin, rifabutin, rifapentin, phenobarbital, and St. John's Wort).
- 11. The subject has experienced any of the following:
 - a. clinically-significant gastrointestinal bleeding within 6 months before the first dose of study treatment

- b. hemoptysis of ≥ 0.5 teaspoon (2.5ml) of red blood within 3 months before the first dose of study treatment
- c. any other signs indicative of pulmonary hemorrhage within 3 months before the first dose of study treatment
- 12. Radiographic evidence of cavitating pulmonary lesion(s)
- 13. Tumor invading or encasing any major blood vessels
- 14. Evidence of tumor invading the GI tract (esophagus, stomach, small or large bowel, rectum or anus), or any evidence of endotracheal or endobronchial tumor within 28 days before the first dose of cabozantinib.
- 15. Uncontrolled, significant intercurrent or recent illness including, but not limited to, the following conditions:
 - a. Cardiovascular disorders including
 - i. Congestive heart failure (CHF): New York Heart Association (NYHA) Class III (moderate) or Class IV (severe) at the time of screening
 - ii. Concurrent uncontrolled hypertension defined as sustained BP > 150 mm Hg systolic, or > 90 mm Hg diastolic despite optimal antihypertensive treatment within 7 days of the first dose of study treatment
 - iii. Any history of congenital long QT syndrome
 - iv. Any of the following within 6 months before the first dose of study treatment:
 - unstable angina pectoris
 - clinically-significant cardiac arrhythmias
 - stroke (including TIA, or other ischemic event)
 - myocardial infarction
 - thromboembolic event requiring therapeutic anticoagulation (Note: subjects with a venous filter (e.g. vena cava filter) are not eligible for this study)
 - b. Gastrointestinal disorders particularly those associated with a high risk of perforation or fistula formation including:
 - i. Any of the following within 28 days before the first dose of study treatment
 - intra-abdominal tumor/metastases invading GI mucosa
 - active peptic ulcer disease; patients must be completely recovered
 - inflammatory bowel disease (including ulcerative colitis and Crohn's disease), diverticulitis, cholecystitis, symptomatic

- cholangitis or appendicitis; patients must be completely recovered from these conditions
- malabsorption syndrome
 - ii. Any of the following within 6 months before the first dose of study treatment:
- abdominal fistula
- gastrointestinal perforation
- bowel obstruction or gastric outlet obstruction
- intra-abdominal abscess. Note: Complete resolution of an intraabdominal abscess must be confirmed prior to initiating treatment with cabozantinib even if the abscess occurred more that 6 months before the first dose of study treatment.
- c. Other disorders associated with a high risk of fistula formation including PEG tube placement within 3 months before the first dose of study therapy
- d. Other clinically significant disorders such as:
 - i. active infection requiring systemic treatment within 28 days before the first dose of study treatment
 - ii. serious non-healing wound/ulcer/bone fracture within 28 days before the first dose of study treatment
 - iii. history of organ transplant
 - iv. concurrent uncompensated hypothyroidism or thyroid dysfunction within 7 days before the first dose of study treatment
 - v. Major surgery within 12 weeks before the first dose of study treatment. Complete wound healing from major surgery must have occurred 1 month before the first dose of study treatment. Minor surgery within 28 days before the first dose of study treatment with complete wound healing at least 10 days before the first dose of study treatment. Subjects with clinically relevant ongoing complications from prior surgery are not eligible.
- 16. Unable to swallow tablets
- 17. A corrected QT interval calculated by the Fridericia formula (QTcF) >500 ms within 28 days before first dose of study treatment. Three ECGs must be performed. If the average of these three consecutive results for QTcF is ≤ 500 msec, the subject meets eligibility in this regard.
- 18. Pregnant or breastfeeding.
- 19. A previously identified allergy or hypersensitivity to components of the study treatment formulation.

- 20. Unable or unwilling to abide by the study protocol or cooperate fully with the investigator or designee.
- 21. Evidence within 2 years of the start of study treatment of another malignancy which required systemic treatment except for cured nonmelanoma skin cancer or cured in situ cervical carcinoma
- 22. Any other severe acute or chronic medical or psychiatric condition or laboratory abnormality which, in the judgment of the investigator, would have made the patient inappropriate for entry into this study.

